#### Table 14Adverse Events of Special Interest

AESI, adverse event of special interest; MedDRA, Medical Dictionary for Regulatory Activities.

### 8.5 Overdose

For this study, any dose of selumetinib greater than the assigned dosage will be considered an overdose. There is currently no specific treatment in the event of overdose of selumetinib, and possible symptoms of overdose are not established.

Overdose should be followed up and treated with appropriate supportive care until recovery.

- An overdose with associated AEs is recorded as the AE diagnosis/symptoms on the relevant AE modules in the eCRF and on the Overdose eCRF module.
- An overdose without associated symptoms is only reported on the Overdose eCRF module.

If an overdose on an AstraZeneca study intervention occurs in the course of the study, the Investigator or other site personnel should inform appropriate AstraZeneca representatives immediately, but **no later than 24 hours** of when he or she becomes aware of it.

The designated AstraZeneca representative works with the Investigator to ensure that all relevant information is provided to the AstraZeneca Patient Safety data entry site within one or 5 calendar days for overdoses associated with an SAE (see Section 8.4.9) and within 30 days for all other overdoses.

### 8.6 Human Biological Samples

Instructions for the collection and handling of biological samples will be provided in the study specific laboratory manual. Samples should be stored in a secure storage space with adequate measures to protect confidentiality. For further details on Handling of Human Biological Samples see Appendix C.

Human blood samples will be disposed as soon as possible after the test outlined in this document is complete.

Pharmacokinetic or PD samples may be disposed of or anonymised by pooling. Additional analyses may be conducted on the anonymised, pooled PK or PD samples to further evaluate and validate the analytical method. Any results from such analyses may be reported separately from the Clinical Study Report.

Remaining unused PK or PD samples may be used for exploratory biomarker analysis as indicated in Section 8.7 and is subject to agreement in the ICF and also according to local requirements.

### 8.6.1 Pharmacokinetics

- Blood samples will be collected for measurement of plasma concentrations of selumetinib and N-desmethyl selumetinib as specified in the SoA (Table 2).
- Samples may be collected at additional time points during the study if warranted and agreed upon between the Investigator and the sponsor, e.g., for safety reasons. The timing of sampling

may be altered during the course of the study based on newly available data (eg, to obtain data closer to the time of peak or trough matrix concentrations) to ensure appropriate monitoring.

- Plasma samples will be used to analyse the PK of selumetinib and N-desmethyl metabolite. Samples collected for analyses of study intervention (plasma) concentration may also be used to evaluate safety or efficacy aspects related to concerns arising during or after the study.
- Pharmacokinetic samples will be analysed at bioanalytical test sites operated by or on behalf of AstraZeneca. Samples will be collected, labelled, stored, and shipped as detailed in the Laboratory Manual.

#### 8.6.1.1 Collection of Samples

Blood samples will be collected for measurement of selumetinib and N-desmethyl selumetinib as shown in Table 15.

r	T.
	Time a
Cycle 1, Day 1 b	Pre-dose and 1, 2, 3, 4, 6, 8, 10-12, and 18-24 hours post-dose
Cycle 2, Day 1 °	Pre-dose and 1, 2, 3, 4, 6, 8, and 10-12 hours post-dose
Cycle 5, Day 1	Pre-dose
Cycle 13, Day 1	Pre-dose
Cycle 25, Day 1	Pre-dose
Transition from granule to capsule formulation d	Pre-dose, 0.5, 1.5, 3, 6, and 10-12 hours post-dose

Table 15Pharmacokinetic Sampling Schedule

a. Pre-dose within 10 minutes prior to dosing. Time allowance for samples 1, 2, 3 and 4 hours post-dose:
 ± 15 minutes, 6 and 8 hours post-dose ± 30 minutes. On Cycle 2, Day 1, the second dose of selumetinib should be taken after the 12 hour sample.

b. Single dose (morning only) will be administered on Cycle 1, Day 1; bid continuous dosing will start from Cycle 1, Day 2.

c. For operational reasons, the pharmacokinetic sampling on Cycle 2, Day 1 can take place on any day between Cycle 1, Day 24 and Cycle 2, Day 8 as long as the participant has received 3 consecutive days of bid dosing immediately prior to the PK day. Every effort should be made to conduct PK sampling within the window. However, if for unforeseen reasons this is not possible, PK sampling can be performed at any time from 7 days prior to Cycle 2, Day 1 to end of Cycle 3 provided the participant has received 3 consecutive days of dosing immediately prior to the PK day.

d. Samples should be taken on Day 7 (range Day 4 to Day 14) as long as the participant has received 3 consecutive days of twice daily dosing with capsule formulation immediately prior to the PK day.

PK, pharmacokinetic.

### 8.6.1.2 Determination of Drug Concentration

Samples for determination of selumetinib and N-desmethyl selumetinib in plasma will be assayed by **CCI** bioanalytical laboratories on behalf of AstraZeneca, using an appropriately validated bioanalytical method. Full details of the analytical method used will be described in a separate bioanalytical report. Incurred sample reproducibility analysis, if any, will be performed alongside the bioanalysis of the test samples. The results from the evaluation, if performed, will be reported in a separate Bioanalytical Report.

#### 8.6.2 **Pharmacodynamics**

Where possible, optional blood samples for exploratory analysis of pharmacodynamic biomarkers in PBMCs can be taken during Cycle 1, Day 1. This analysis includes, but may not be limited to, pERK inhibition. This would require additional blood volume on a PK profile day, in addition to the volume required for PK samples and for safety samples. In line with the European Condition requirement that blood volume should not exceed 1% of the total blood volume at any single time, the samples for pERK can only be collected only in patients  $\geq 27$  kg. For a patient that is 6 years old this would mean that they would have to be approaching the 98th percentile on the UK-WHO growth chart (UK WHO Growth Chart). It is therefore considered these samples would be collected only in the oldest and largest of children. Samples should be taken according to Table 16.

#### Pharmacodynamic Sampling Schedule Table 16

Visit	Time a
Cycle 1, Day 1	Pre-dose and 1, 3 and 18-24 hours post-dose
a. Dre dose within 10 mi	nutes prior to dosing. Time allowance for samples 1 and 3 hours post dose $\pm 15$ minut

Pre-dose within 10 minutes prior to dosing. Time allowance for samples 1 and 3 hours post-dose  $\pm$  15 minutes.

#### 8.7 Human Biological Sample Biomarkers

#### 8.7.1 **Collection of Mandatory Samples for Biomarker Analysis**

There is no additional biomarker sample collection in this study.

#### 8.7.2 **Other Study-related Biomarker Research**

Already collected PK or PD samples may be analysed to explore potential biomarkers, which may influence the progression of NF1 and inoperable PNs (and associated clinical characteristics) and/or identify participants likely to respond to selumetinib or may be surrogate markers of response. Exploratory biomarker analyses may include (but not limited to) phosphorylated ERK, cytokines, and/or quantification of RNA expression using quantitative RT-PCR, microarray, or other technology in blood, peripheral blood mononuclear cells, serum, or plasma to evaluate their association with observed responses to selumetinib. This analysis excludes genomic analysis, but targeted sequence analysis on genes involved in NF1 might be included. This biomarker research is subject to additional optional consent in the ICF.

For storage, re use, and destruction of biomarkers samples, see Section 8.6.

#### 8.8 **Optional Genomics Initiative Sample**

Not applicable.

# 8.9 Health Economics

Not applicable.

# 9 STATISTICAL CONSIDERATIONS

# 9.1 Statistical Hypotheses

No formal hypotheses will be tested.

The primary PK objective of the study is to estimate the granule formulation single dose AUC0-12 for the final recommended dose schema in paediatric participants aged  $\geq 4$  to < 7 years and aged  $\geq 1$  to < 4 years and check the estimation with the capsule formulation single dose AUC0-12 at 25 mg/m^2 as observed in the pivotal safety and efficacy study SPRINT.

# 9.2 Sample Size Determination

### **Global Cohorts (Cohorts 1 and 2)**

Approximately  $\stackrel{\text{cc}}{=}$  participants will be dosed in Cohorts 1 and 2 to achieve  $\stackrel{\text{cc}}{=}$  evaluable participants at the recommended granule formulation dose schema, of whom at least  $\stackrel{\text{cc}}{=}$  participants will be aged  $\geq 1$  to < 4 years (with at least  $\stackrel{\text{cc}}{=}$  aged < 2 years) and at least  $\stackrel{\text{cc}}{=}$  participants will be aged  $\geq 4$  to < 7 years. A sample size of  $\stackrel{\text{cc}}{=}$  participants will provide reasonable precision to characterise PK and safety.

At least evaluable participants in each age group are required at the final recommended granule formulation dose schema.

With a minimum of evaluable participants in each age group and evaluable participants in total, the numbers of participants in the 2 age groups will fall between a combination of **CCI** to a combination of **CCI**. With sample sizes of **CCI** in an age group, the power to show that the  $^{60}$  % CI of the AUC0-12 geometric mean falls within the acceptance range **CCI** -fold of the SPRINT AUC0-12 geometric mean; FDA Guidance 2014) will be 90%, 99.9% and > 99.9%, respectively. The power for two age groups falling within the acceptance range simultaneously will therefore be 90% × 99.9%  $\approx$  90% and 99.9% × 99.9%  $\approx$  99.9% for the **CCI** combination and **CCI** combination, respectively. This sample size calculation assumes that there is a  $^{60}$  % difference in exposure between the granule and capsule formulation and assumes an inter-subject gCV% of % (Wang et al 2012). The choice of gCV% is based on observations from Study 89 ( $^{60}$  %) and the SPRINT study ( $^{60}$  %).

In the dose-finding phase of this study, the exposure AUC0-12 will be monitored on an ongoing basis. The minimum sample size for each cohort and the study may be re-estimated when evaluable participants in that cohort have provided acceptable PK exposures. The re-estimation will use the observed inter-subject gCV%. Table 17 below shows the minimum sample sizes required in each age group corresponding to different variability and different scenarios.

# Table 17Sample Size Estimations based on Inter-subject gCV% and Expected
Differences in AUC0-12 between SPRINKLE and SPRINT studies

Inter-subject gCV%	Difference in AUC0-12 between SPRINKLE and SPRINT studies		
	± 5%	± 10%	± 15%
CCI			
-			

AUC0-12, area under the concentration-time curve from time zero to 12 hours; CV, geometric coefficient of variation.

### Japan Cohort

In addition to the Global Cohorts (Cohorts 1 and 2), a separate Japan Cohort of a minimum of evaluable Japanese participants aged  $\geq 1$  to < 7 years will be recruited in Japan.

An evaluable participant for PK and sample size calculations is defined as a participant with a PK profile on Day 1 (for an individual at least 6 samples during the 12-hour time period post first dose on Cycle 1, Day 1 and must include the 10-12 hour PK sample) without any important protocol deviations potentially impacting the PK results.

**Note**: "Enrolled" means a participant's or their legally authorised representative (parent or guardian) and participant's (if deemed appropriate as per local regulations) agreement to participate in a clinical study following completion of the informed consent process. Potential participants who are screened for the purpose of determining eligibility for the study, but do not receive selumetinib, are considered "screen failures", unless otherwise specified by the CSP.

# 9.3 **Populations for Analyses**

The populations are defined as shown in Table 18.

Population/Analysis set	Description
All Enrolled	All participants who sign the ICF
Pharmacokinetic Analysis Set	All participants who receive at least one dose of selumetinib and who have at least one post-dose quantifiable plasma concentration with no important protocol deviations
Safety Analysis Set	All participants who receive at least one dose of selumetinib

Table 18Populations for Analysis

ICF, informed consent form.

Note: The PK data for the Japan Cohort will be summarised separately to the PK data for the Global Cohorts.

In the case of an important protocol deviation or events that may impact the quality of the data, affected PK data collected will be excluded from the summaries and statistical analyses, but will CONFIDENTIAL AND PROPRIETARY 85 of 168

Clinical Study Protocol -5.0 Selumetinib - D1346C00004 still be reported in the study result listings. Important deviations will be listed and summarised in the Clinical Study Report. The study physician, pharmacokineticist, and statistician will agree on the strategy for dealing with data affected by protocol deviations or events that may impact the quality of the data before any statistical analysis is performed.

#### 9.4 **Statistical Analyses**

The Statistical Analysis Plan will be finalised prior to database lock and will include a more technical and detailed description of the statistical analyses described in this section. This section is a summary of the planned statistical analyses of the most important endpoints including primary and key secondary endpoints.

#### 9.4.1 **General Considerations**

All study data, originally captured or derived, will be listed and summarised as appropriate.

In the rest of this section, the planned analyses are general and will be performed both for Global Cohorts and Japan Cohort. If an analysis is particular for one population (for example the granule/capsule PK exposure comparison), it will be stated so.

The PK analysis will be based on the PK analysis set. Plasma concentrations and all PK parameters derived from plasma concentrations will be listed and summarised. In the case of an important protocol deviation or event, affected PK data may be excluded from the summaries and statistical analyses, but will still be included in the data listings. The PK exclusion decision will be documented by the PK scientist including the reason(s) for exclusion. PK analyses for the Japan Cohort will be presented separately from the Global Cohorts.

The safety analyses will be based on the safety analysis set. Continuous variables will be summarised using descriptive statistics (n, mean, SD, minimum, median, maximum). Categorical variables will be summarised in frequency tables (frequency and proportion). There are no statistical analyses other than summary statistics planned for safety endpoints.

Participant disposition will be presented for all enrolled participants. Protocol deviations will be discussed at the data review meeting before database lock and will focus on deviations from the CSP including (but not limited to):

- Inclusion/exclusion criteria deviations •
- Dosing deviations •
- Time window deviations for PK or safety assessments ٠
- Receiving prohibited concomitant medications •
- Other procedural and study conduct deviations

Efficacy evaluation will be based on the safety set using PN response data from volumetric MRI.

All statistical analyses and production of tables, figures and listings will be performed using CONFIDENTIAL AND PROPRIETARY 86 of 168

There will be 3 analysis time points:

- 1 Pharmacokinetic, dose-finding, and primary safety analysis:
  - A DCO (DCO1) and analysis will occur after all participants have had the opportunity to complete 3 cycles of treatment. This primary analysis will confirm the recommended granule formulation dose schema and assess PK, safety/tolerability and palatability. The timing of DCO1 may be different for the Global Cohorts (Cohorts 1 and 2) from the Japan Cohort, based on their date of Last Subject In.
  - The PK samples will be analysed on a regular basis to inform SRC. It is expected that single and multiple dose PK from all participants dosed with selumetinib would be available within 3 months of the last participant being dosed; at this point, all participants will have palatability data available and a minimum of 3 months of safety data.
- 2 Safety and efficacy of the granule formulation:
  - A DCO (DCO2) and analysis will occur after all participants in the study (Global and Japan Cohorts) have had the opportunity to complete 25 cycles (or terminated selumetinib); this analysis will provide additional PK and safety/tolerability data, as well as palatability and efficacy data.
  - Efficacy analyses will be performed, including: ORR (assessed by ICR and investigator),
    CCI and COAs.
- 3 Long term safety follow-up for participants until they reach the age of 5 years or commence an alternative systemic NF1-PN treatment, whichever is the earlier:
  - A final analysis will occur when all participants in the study (Global and Japan Cohorts) have had the opportunity to complete their last assessment in the study, including the safety follow-up for participants aged < 5 years.

  - All of the safety/tolerability analyses will be updated with the data captured after the DCO for the analysis shown in bullet point 2 above (safety and efficacy of the granule formulation).

#### 9.4.2 Pharmacokinetic Assessments

#### 9.4.2.1 **Primary and Secondary Endpoint(s)**

Pharmacokinetic parameters will be derived for selumetinib using plasma concentrations.

Selumetinib PK is not time-dependent and minimal accumulation was observed in adult or paediatric participants following chronic bid dosing. In addition, sample size calculations have been based on single dose PK variability from Study 89. Therefore, single dose AUC0-12 will be used as the primary PK variable for comparison with SPRINT data.

Summary statistics including gCV%, arithmetic mean (SD), median (min, max) will be provided by age and BSA group. The geometric mean is calculated as the exponential of the arithmetic mean

Clinical Study Protocol -5.0 AstraZeneca Selumetinib - D1346C00004 calculated using log-transformed data. The gCV% is calculated as  $100 \sqrt{\exp(s^2) - 1}$  where s is the SD of the log-transformed data.

At the final sample size for the recommended dose schema in the Global Cohorts (Cohorts 1 and 2), the AUC0-12 geometric mean and % CI (from one sample t-statistic) will be determined for each age group and overall. If the % CI falls within CCI % of the geometric mean AUC0-12 observed in the pivotal safety and efficacy study, SPRINT, then it will be concluded that comparable exposure to selumetinib was observed across the age groups.

Box and whisker plots of observed AUC0-12 will be produced for comparison to the target range for the capsule formulation determined from SPRINT.

#### 9.4.2.2 Secondary Endpoint(s)

Pharmacokinetic parameters will be derived for selumetinib and N-desmethyl selumetinib using plasma concentrations.

The following secondary PK parameters will be calculated, if appropriate, and if data allow:

- Plasma concentrations and PK parameters of selumetinib including, but not limited to:
  - AUC0-12 derived after multiple dose administration.
  - Cmax, AUC0-6, AUClast, CL/F, tmax, tlast; derived after single and multiple dose administration.
  - AUC0-24, Vz/F and  $t\frac{1}{2}\lambda z$  after single dose administration.
  - Rac Cmax, Rac AUC0-12, and Vss/F derived after multiple dose administration.
- Plasma concentrations and PK parameters of N-desmethyl selumetinib, including, but not limited to:
  - Cmax, AUC0-6, AUC0-12, AUClast, tmax, tlast derived after single and multiple dose administration.
  - Rac Cmax and Rac AUC derived after multiple dose administration.
  - Parent-to-metabolite ratio for AUC0-6, AUC0-12 and AUC0-24 (single dose only) and Cmax derived after single and multiple dose administration.

For the participants that transition to capsule formulation BSA normalised AUC0-6, AUC0-12, AUClast and Cmax will be determined following multiple dose administration of granule and capsule formulation. The ratio of granule:capsule formulation will be determined for each of these parameters, the data will be listed and summarised.

Summary statistics including geometric mean (geometric CV%), arithmetic mean (SD), median (min, max) will be provided by formulation, analyte and period for AUC0-6, AUC0-12, AUC0-24, AUClast and Cmax. For CL/F, Rac Cmax, Rac AUC0-12 and for the comparisons of BSA normalised PK parameters for capsule and granule only arithmetic mean (SD) and median (min,

Clinical Study Protocol -5.0 Selumetinib - D1346C00004 max) will be presented. For tmax and tlast, only median (min, max) will be presented. For CL/F,  $t^{1/2}\lambda z$ , Vss/F and Vz/F only arithmetic mean (SD) and median (min, max) will be presented.

Selumetinib and N-desmethyl selumetinib plasma concentrations and PK parameters will be listed and summarised by formulation, age group, dose group and BSA group for Cycle 1 Day 1, Cycle 2 Day 1 and capsule dosing Day 7 (range Day 4 to 14).

Geometric mean (± geometric SD) plasma concentration versus nominal sampling time will be plotted in a linear and semi-logarithmic scale for each PK sampling period and with a separate plot for each analyte. Exploratory analyses may be conducted to explore the relationship between exposure or PK parameters, PBPK simulations and the pharmaceutical properties of the API and/or the formulation.

Box and whisker plots of observed PK parameters will be produced for comparison to the target range for the capsule formulation determined from SPRINT.

Further data presentation and reporting details will be provided in the Statistical Analysis Plan.

Details of **CC** analyses will be described in the **CC** finalised before database lock. The CC analyses will be presented separately from the main Clinical Study Report.

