### **Rationale:**

Selumetinib (capsule formulation) is approved by the FDA for the treatment of paediatric patients 2 years of age and older with NF1 who have symptomatic, inoperable PN and a Conditional Marketing Authorisation was granted in Europe/EEA for paediatric patients 3 years of age and older, via the European Centralised Procedure on 17 June 2021. The efficacy of selumetinib in the treatment of NF1-related inoperable PN in paediatric participants was demonstrated in the SPRINT study; safety data from this study showed that selumetinib has a manageable safety profile with favourable tolerability over several years of treatment in this population.

Selumetinib is currently available in a capsule formulation which precludes administration to children with a BSA of  $< 0.55 \text{ m}^2$  or very young children who may have difficulty swallowing capsules. Therefore, AstraZeneca has developed an alternative age appropriate granule formulation of selumetinib for infants and young children aged  $\ge 1$  to < 7 years which is contained within a sprinkle capsule.

The relative bioavailability of the granule and capsule formulations has been investigated in adult healthy male subjects (Study D1532C00089, Study 89); with a geometric mean ratio (90% CI) of 0.654 (0.581, 0.736) for dose-normalized Cmax and 0.865 (0.811, 0.922) for dose-normalized AUC. The selumetinib content in the granule formulation batch used in Study 89 was %% therefore, when corrected for selumetinib content, the granule AUC was only %% lower compared to capsule. The selumetinib content in the granule formulation which will be used in the SPRINKLE study will be approximately %%.

This study is designed to define a dosing regimen and assess the PK and safety of the granule formulation in children aged  $\geq 1$  to < 7 years; the study will also include descriptive analyses of exploratory efficacy endpoints. Assuming that the AUC for the granule formulation is similar to the AUC for the capsule formulation observed in SPRINT, efficacy in children aged

 $\geq$  1 year can be extrapolated from the SPRINT study. The study will inform the benefit risk profile of the granule formulation in children aged  $\geq$  1 to < 7 years with NF1-related symptomatic, inoperable PN.

	Objectives		Endpoints
Prima	ary		
•	To determine the PK of selumetinib after administration of the selumetinib granule formulation.	•	Selumetinib AUC0-12 derived after single dose administration.

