3.3 General Considerations

The below mentioned general principles will be followed throughout the study:

- Descriptive statistics will be used for all variables, as appropriate. Continuous variables will be summarised by the number of observations, mean, standard deviation, minimum, Q1, median, Q3, and maximum. For log-transformed data, it is more appropriate to present geometric mean, geometric coefficient of variation, median, minimum, and maximum. Categorical variables will be summarised by frequency counts and percentages for each category.
- For continuous data, the minimum and maximum will be displayed with the same accuracy as the original data. For laboratory data where decimal precision is provided, the maximum and minimum will be displayed to the standard decimal precision. The mean, median, Q1, and Q3 will be rounded to one additional decimal place compared to the minimum/maximum. The standard

deviation will be rounded to 2 additional decimal places compared to the minimum/maximum.

- For categorical data, percentages will be rounded to one decimal place with the exception of **CCI**, which is presented as a whole number. For 0 results, the percentages will not be included, and only 0 will be presented as a result of the categorical variable.
- Unless otherwise stated, percentages will be calculated out of the population total for the corresponding treatment group.
- Descriptive summaries for all endpoints will be based on the planned visit schedule unless otherwise stated.
- SAS® version 9.4 or above will be used for all analyses.

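### The protocol plans no geometric mean or confidence interval for the accumulation ratios or the within-child granule:capsule ratio

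*Protocol*

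**What the plan says.** Protocol 9.4.2.2 treats the PK parameters and their ratios differently.

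- For AUC0-6, AUC0-12, AUC0-24, AUClast and Cmax: "Summary statistics including geometric mean (geometric CV%), arithmetic mean (SD), median (min, max) will be provided by formulation, analyte and period".
- For the ratios, the rule is narrower: "For CL/F, Rac Cmax, Rac AUC0-12 and for the comparisons of BSA normalised PK parameters for capsule and granule only arithmetic mean (SD". The sentence goes on to the median with its range, and after a page break it ends "max) will be presented. For tmax and tlast, only median (min, max) will be presented". Rac Cmax and Rac AUC0-12 stand in the same sentence. They and the granule:capsule comparison therefore get an arithmetic mean (SD) and a median (min, max), and nothing else.
- For children who move to capsules: "The ratio of granule:capsule formulation will be determined for each of these parameters, the data will be listed and summarised".

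The SAP does not settle the statistic. Section 4.4.2.2 says the ratio will be listed and summarised without naming one. Section 4.4.2 refers descriptive statistics to a standard whose name is redacted. Section 3.3 gives ordinary means and quartiles as the default for continuous variables and adds: "For log-transformed data, it is more appropriate to present geometric mean". It does not say whether a ratio counts as log-transformed. Section 2 declares no change to the analyses planned in the protocol.

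The two documents also differ on the ratio itself. The protocol summarises BSA-normalised comparisons. SAP 4.4.1 derives the ratio for both BSA-normalised and dose-normalised parameters, but SAP 4.4.2.2 summarises only the dose-normalised one.

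**The concern.** Each of these quantities is one positive, right-skewed PK value divided by another from a different occasion in the same child. Its natural centre is the geometric mean. The arithmetic mean always lies above it when the ratios vary, and it does not invert. If one child's ratio is 0.5 and another's is 2, the arithmetic mean is 1.25 whichever formulation is the numerator, while the geometric mean is 1.

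The figures a reader would set beside these ratios are geometric. The protocol's Rationale reports Study 89 as a "geometric mean ratio (90% CI) of 0.654 (0.581, 0.736) for dose-normalized Cmax and 0.865 (0.811, 0.922) for dose-normalized AUC", and SAP 4.2.1.1 analyses the primary AUC0-12 by geometric mean and CI.

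Two readings are at stake. Rac, a secondary endpoint, bears on the premise of minimal accumulation that protocol 6.1.2.1 and 9.4.2.1 give for a single-dose primary variable. The granule:capsule ratio is the only within-child comparison of the two formulations. An upward-biased mean and an interval-free median are a weak basis for either.

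**Working it through.** **Inputs from the documents.** Study 89 ratios: AUC 0.865 (0.811, 0.922) and Cmax 0.654 (0.581, 0.736). Protocol 9.4.2.1 defines gCV as sqrt(exp(s²) − 1), where s is the SD of the log data.

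**Assumed, because not given.** The gCV of the within-child ratio and the number of children who transition. Both are shown as ranges.

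**Step 1: is the Study 89 figure on the geometric scale?** A geometric mean ratio is the geometric midpoint of its interval.
- AUC: sqrt(0.811 × 0.922) = 0.8647, matching 0.865. The arithmetic midpoint is 0.8665.
- Cmax: sqrt(0.581 × 0.736) = 0.6539, matching 0.654. The arithmetic midpoint is 0.6585.

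**Step 2: size of the bias.** For a log-normal ratio, arithmetic mean = geometric mean × exp(s²/2) = geometric mean × sqrt(1 + gCV²). The median equals the geometric mean.

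| Ratio gCV | Factor (also the expected mean if true Rac is 1) | True 0.865 | True 0.654 |
|---|---|---|---|
| 20% | 1.02 | 0.88 | 0.67 |
| 30% | 1.04 | 0.90 | 0.68 |
| 40% | 1.08 | 0.93 | 0.70 |
| 50% | 1.12 | 0.97 | 0.73 |

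**Step 3: when would the expected arithmetic mean reach 1?** Solve true ratio × sqrt(1 + gCV²) = 1.
- AUC: gCV = sqrt(1/0.865² − 1) = 58%.
- Cmax: gCV = sqrt(1/0.654² − 1) = 116%.

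If the two occasions vary independently, the factor is 1 + CV² per occasion. The thresholds are then a per-occasion CV of about 40% and 73%.

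**Step 4: how variable was the adult ratio?** Assume a two-period crossover with n − 2 degrees of freedom and n from 12 to 48. The SD of the log ratio is sqrt(n) × (half the log width of the 90% CI) / t. This gives a ratio gCV of 12% to 27% for AUC and 23% to 52% for Cmax. The expected arithmetic means would be 0.87 to 0.90 and 0.67 to 0.74.

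**Step 5: small samples.** Simulation with 200,000 samples, true ratio 0.865, ratio gCV 40% and n = 8. The chance that the summary is at or above 1 is 28% for the arithmetic mean, 18% for the median and 14% for the geometric mean. The arithmetic mean is at or above 1 while the median is below 1 in 13% of samples. With a true ratio of 0.654, each of these chances is 0.5% or less.

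**Step 6: what an interval would add.** With the same gCV and n, s = sqrt(ln 1.16) = 0.385. The 95% half-width on the log scale is 2.365 × 0.385 / sqrt(8) = 0.322, a factor of 1.38. An observed geometric mean of 0.865 would carry an interval of about 0.63 to 1.19. A median alone does not convey that uncertainty.

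**Step 7: do the two normalised ratios agree?** Dividing the BSA-normalised granule:capsule ratio by the dose-normalised one leaves the granule mg/m² dose over the capsule mg/m² dose. They coincide only if that dose is the same at both visits. The granule dose levels are redacted, so the gap cannot be sized.

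**The case against.** A reader who stops at the page break might infer that these ratios are summarised by arithmetic mean alone. The full sentence does not support that: the median and range are planned too. Under log-normality the median targets the same quantity as the geometric mean and inverts in the same way. The individual ratios are also listed.

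A reader might also infer that the arithmetic mean could conceal a granule shortfall as large as the one in adults. In expectation that needs a ratio gCV of 58% for AUC or 116% for Cmax. It can happen by chance for AUC in a small group, but hardly for Cmax, and the median and listings would sit beside the mean.

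Other points against also have force.
- The granule:capsule ratio belongs to an exploratory objective (protocol section 3).
- An inflated Rac overstates accumulation, so it works against the sponsor's premise.
- Study 89 enrolled healthy adult men and used a batch whose selumetinib content differed, so no choice of mean makes the comparison exact.
- The SAP leaves the statistic open, and the redacted standard may supply a geometric mean.

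These points limit the consequence. They do not supply what is missing. No interval is planned for the ratios. The geometric means by formulation are not stated to be confined to the children who transition, and their quotient equals the paired ratio only if the same children contribute to both. A standard that cannot be read cannot be relied on to override the protocol's explicit wording.

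**Conclusion.** The point holds as a minor one. The protocol restricts Rac Cmax, Rac AUC0-12 and the granule:capsule comparison to arithmetic mean (SD) and median (min, max), with no geometric mean, gCV% or CI. The mean is biased upward by about 2% to 12% over an assumed ratio gCV of 20% to 50%, and it is not on the scale of the results it would be read against. The median avoids that bias but has no interval, and SAP 4.4.2.2 allows a summary from as few as three children.

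The sizes rest on log-normal ratios, on assumed variability and numbers, and, for the adult range, on an assumed crossover design. The primary conclusion, which rests on single-dose AUC0-12, is unaffected. The disagreement over which normalised ratio is summarised is a separate inconsistency and needs no assumption.

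**What to change.** In protocol 9.4.2.2 and SAP 4.4.2.2, state that Rac Cmax, Rac AUC0-12 and the individual granule:capsule ratios are summarised by geometric mean, gCV% and a 95% CI. Compute the CI on the paired log ratio and back-transform it. Keep the median and range; the arithmetic mean (SD) may stay as an optional column.

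In the same edit, name in both documents which ratio is summarised: BSA-normalised, dose-normalised or both. If comparison with Study 89 is intended, note that its ratios are dose-normalised.

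The cost is a few lines of wording and a small change to the table shells. No new data are needed. Intervals will be wide if few children transition, but that width is information the reader needs.
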